## 5 STUDY ENROLLMENT AND WITHDRAWAL

The study will recruit potential subjects 18 years of age or older who are suspected to have LRTI. In order to meet the primary objective, the study requires 560 evaluable subjects (approximately 280 per group). Taking into account subjects who withdraw, fail to complete Visit 3, or do not meet other inclusion criteria for the ATP population at Day 5 as defined in Section 11.4, this study will randomize approximately 674 enrolled subjects (approximately 337 per group) with PCT  $\leq 0.25$  ng/milk. Potential subjects will be recruited from hospital-based outpatient settings including EDs and clinics within our study sites in North Carolina (Duke University Hospital, Durham VA Medical Center), Georgia (Emory University Hospital and Atlanta VA Medical Center), New York (University of Rochester) and Texas (Houston VA Medical Center).

Clinical research personnel will approach patients meeting the clinical criteria (see inclusion criteria below) to discuss the study with them. Those who agree to participate will be consented for study enrollment and for future use samples. Declination to participate in collection of future use samples will not affect participation in the primary study. All enrolled subjects will have samples obtained including blood for PCT measurements and nasopharyngeal swabs for etiology testing. Subjects with a PCT  $\leq 0.25$  ng/mL will be randomized 1:1 to receive oral azithromycin or placebo.

Subjects with a PCT  $> 0.25$  ng/mL will not be randomized and will not receive study treatment. These subjects will have their charts reviewed for roughly 28 days after enrollment. Providers will be notified that the patient will not be randomized and therefore, the treating provider should make treatment decisions.

This type of consenting ensures that only patients who are willing to proceed to randomization and subsequent study activities are screened for PCT levels. Potential subjects will be identified at any time following clinical diagnosis of LRTI. Other forms and/or mechanisms of recruitment may also be used. The local IRB will approve recruitment materials prior to use.

A study clinician licensed to make medical diagnoses must confirm the subject meets Inclusion and Exclusion Criteria. No exemptions are granted on Subject Inclusion/Exclusion Criteria in DMID-sponsored studies. Questions about eligibility will be directed toward the DMID Medical Officer.

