### 11.2 Sample Size Considerations:

The study will be powered to the primary endpoint of clinical improvement with 560 participants included in the according-to-protocol analysis population at Day 5. To achieve this sample size, approximately 674 enrolled subjects will need to be randomized (1:1) to placebo or azithromycin treatment to have 80% power to rule out a 12.5% increase in the clinical improvement rate with antibiotic therapy compared to placebo assuming a clinical improvement rate of 57.6% in each group using a two-sided 95% confidence interval with continuity correction, in a per-protocol analysis (i.e., allowing for 16.9% loss in each treatment group to follow up/rescue medication).

The primary analysis will include an intention-to-treat (ITT) estimation of the difference in proportions of subjects with clinical improvement at Day 5 in the antibiotic and placebo groups with a two-sided 95% confidence interval.

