8.2.8. Analysis of DOOR at D5V Using ITT and ATP-5 Analysis Populations

DOOR at D5V is defined in Section 3.3.

The null hypothesis corresponding to this analysis is:

H0: The sum of the probability that a subject assigned to placebo will have a higher DOOR at D5V Visit than if assigned to the Azithromycin plus one-half the probability of equal DOORs at D5V is 50% (i.e., no difference in DOOR at D5V).

The above null hypothesis can be tested using a Mann-Whitney U Test.

This analysis will use multiple imputation with a linear model to impute missing DOOR at D5V. Details of multiple imputation methods are described in Section 8.4.2.

For each of the 20 complete multiple imputation datasets, a Mann-Whitney U statistic will be computed using randomization to placebo versus randomization to azithromycin to define the binary grouping and DOOR at D5V as the outcome. The U statistics are asymptotically normal distributed, and so they can be combined into a single test statistic using Rubin's Rules [3].

Defining the following:

n_1 : number of subjects in ITT population randomized to placebo

n_2 : number of subjects in ITT population randomized to Azithromycin

m : number of imputed datasets ($m = 20$)

Q_i : U statistic computed from the i^{th} multiply imputed dataset

$$\bar{Q} = \frac{1}{m} \sum_{i=1}^m Q_i$$

Q_0 : the expected value of a U statistic under the null hypothesis ($Q_0 = \frac{n_1 n_2}{2}$)

\bar{U} : The within imputation variance (this is not the mean of the U statistics). Correcting for ties, the formula for the within imputation variance of the Mann-Whitney U statistic is:

$$\bar{U} = \text{Var}(Q_i) = \frac{n_1 n_2}{12} \left[(n_1 + n_2 + 1) - \frac{1}{(n_1 + n_2)(n_1 + n_2 + 1)} \sum_{c=1}^D (M_c^3 - M_c) \right]$$

[2 and 4]

where M_c is the number of tied ranks for the c^{th} value DOOR in the dataset and D is the number of distinct values of DOOR in the dataset. Because the numbers of tied ranks should be very similar across the 20 multiply imputed datasets, the number of ties will be counted from the first imputed dataset only, and those counts will be used to compute the corrected variance.

$$B = \frac{1}{m-1} \sum_{i=1}^m (Q_i - \bar{Q})^2$$

$$T = \bar{U} + \frac{m+1}{m} B$$

$$W = \frac{(\bar{Q} - Q_0)^2}{T}$$

$$r = \frac{m+1}{m} \frac{B}{\bar{U}}$$

$$\nu = (m-1) \left(1 + \frac{1}{r} \right)^2$$

Under null hypothesis corresponding to the secondary DOOR analysis of this study,

$$W \sim F_{1,\nu}$$

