This F-distribution is used to compute a p-value (one-sided probability) from the overall test statistic W . The null hypothesis will be rejected if $p < 0.05$.

A corresponding 95% CI for U will be computed using the overall test statistic W through the inversion of the F-test. Dividing the bounds of this CI by $n_1 n_2$ will yield the bounds for the 95% CI of $\text{Pr}(\text{Higher DOOR in placebo}) + 0.5 \text{Pr}(\text{Equal DOOR in azithromycin})$. Thus, the CI for DOOR probability is given by:

$$95\% \text{ CI: } \left(\frac{\bar{Q} - \sqrt{T \times F_{0.95,1,\nu}}}{n_1 n_2}, \frac{\bar{Q} + \sqrt{T \times F_{0.95,1,\nu}}}{n_1 n_2} \right)$$

A point estimate of the DOOR probability will be obtained by dividing \bar{Q} by $n_1 n_2$. Results will be shown in [Table 37](#) for ITT population.

Analysis of DOOR will be repeated for the ATP-5 analysis population and using the same multiple imputation model as ITT analysis. Results of this analysis will be reported in [Table 38](#).

Additional analyses of DOOR at D5V will be performed using only subjects in the ATP-5 population with complete data. These analyses will test the null hypotheses described above using the Mann-Whitney U Test, estimate $\Pr(\text{Higher DOOR in placebo}) + 0.5 \Pr(\text{Equal DOOR})$ using U divided by the number of pairwise comparisons, and will compute confidence intervals by (1) inverting the Mann-Whitney U Test and (2) using a non-parametric bootstrap.

Confidence intervals from inverting the Mann-Whitney U Test will be given by:

$$\left(\frac{U}{n_1 n_2} - 1.96 \times \sqrt{\frac{\text{Var}(U)}{(n_1 n_2)^2}}, \frac{U}{n_1 n_2} + 1.96 \times \sqrt{\frac{\text{Var}(U)}{(n_1 n_2)^2}} \right)$$

Correcting for ties, the formula for the variance of U is:

$$\text{Var}(U) = \frac{n_1 n_2}{12} \left[(n_1 + n_2 + 1) - \frac{1}{(n_1 + n_2)(n_1 + n_2 + 1)} \sum_{c=1}^D (M_c^3 - M_c) \right]$$

where M_c is the number of tied ranks for the c^{th} value DOOR in the dataset and D is the number of distinct values of DOOR in the dataset.

Confidence intervals for the DOOR probability using a non-parametric bootstrap:

$$\left(\frac{U_{0.025}}{n_1 n_2}, \frac{U_{0.975}}{n_1 n_2} \right)$$

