
Table with similar format:

Table 36: Improvement in LRTI Symptoms or Fever at D28V - ATP-28 Analysis Population

[Implementation Note: Update the footnote to use ATP-28.]

Table 37: ITT Analysis of DOOR at Day 5 - ITT Analysis Population

Statistic	Value
Subjects with all DOOR components measured – n (%)	x (x)
Subjects with one or more DOOR components imputed – n (%)	x (x)
Pr(Higher DOOR in Placebo Arm) ^a (95% CI) ^a	x.xx (x.xx, x.xx)
P-value ^b	x.xxx

^aProbability of Higher DOOR in Placebo Arm at D11V + 0.5 Probability of Equal DOOR. 95% CI obtained through inversion of the F-test used to compute the p-value.
 
^bP-value obtained by Mann-Whitney U Test. P-value boundary of 0.05 is used to conclude statistical significance. It is important to note that conclusions from DOOR analyses must rely on a detailed assessment of the DOOR components as well as consideration of sensitivity analyses, in addition to the statistical test described in this table.
	

Table 38: According-to-Protocol Analysis of DOOR at D5V - ATP-5 Analysis Population

Statistic	Value
Subjects with all DOOR components measured – n (%)	x (x)
Subjects with one or more DOOR components imputed – n (%)	x (x)
Pr(Higher DOOR in Placebo Arm) ^a (95% CI) ^a	x.xx (x.xx, x.xx)
P-value ^b	x.xxx
^a Probability of Higher DOOR in Placebo Arm at D11V + 0.5 Probability of Equal DOOR. 95% CI obtained through inversion of the F-test used to compute the p-value. ^b P-value obtained by Mann-Whitney U Test. P-value boundary of 0.05 is used to conclude statistical significance. It is important to note that conclusions from DOOR analyses must rely on a detailed assessment of the DOOR components as well as consideration of sensitivity analyses, in addition to the statistical test described in this table.	

Table 39: Deterioration in LRTI Symptoms at D5V - ATP-5 Analysis Population

Symptom	Azithromycin				Placebo				Difference (95% CI) ^b	P-Value ^c
	N	n	%	95% CI ^a	N	n	%	95% CI ^a		
Any Symptom	x	x	x	(x.x, x.x)	x	x	x	(x.x, x.x)	xx (x.x, x.x)	x.xxx
Cough	x	x	x	(x.x, x.x)	x	x	x	(x.x, x.x)	xx (x.x, x.x)	x.xxx
Sputum Production	x	x	x	(x.x, x.x)	x	x	x	(x.x, x.x)	xx (x.x, x.x)	x.xxx
Chest Pain	x	x	x	(x.x, x.x)	x	x	x	(x.x, x.x)	xx (x.x, x.x)	x.xxx
Difficulty Breathing	x	x	x	(x.x, x.x)	x	x	x	(x.x, x.x)	xx (x.x, x.x)	x.xxx

N = Number of subjects in the ATP-5 analysis population and the respective treatment group having the symptom at baseline with non-missing severity.

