Missing ^b	xx	xx (xx, xx)	xx	xx (xx, xx)

N = Number of subjects in the ITT Population in the given treatment group.

^a95% CI estimated using the Wilson Method.

^bNumber of subjects missing clinical improvement at all three timepoints (D5V, D11V, D28V) will be classified as missing.

Table 53: ITT Analysis of DOOR Based on Number of Times Clinical Improvement was Achieved Across D5V, D11V, and D28V - ITT Analysis Population with Complete Data

Tie-Breaking	Statistic	Value
No tie-breaking	Subjects with non-missing DOOR– n (%)	x (x)
	Pr(Higher DOOR in Placebo Arm) ^a (95% CI) ^b	x.xx (x.xx, x.xx)
	P-value ^c	x.xxx
Duration of antibiotic use as tie-breaker	Subjects with non-missing DOOR– n (%)	x (x)
	Pr(Higher DOOR in Placebo Arm) ^a (95% CI) ^b	x.xx (x.xx, x.xx)
	P-value ^c	x.xxx

Note: DOOR was calculated based on subjects with non-missing clinical improvement for at least one of the timepoints.
^aProbability of Higher DOOR in Placebo Arm + 0.5 Probability of Equal DOOR. CI obtained through inversion of the F-test used to compute the p-value.
^bObtained through using inversion of the Mann-Whitney U test with a normal approximation and assuming the null hypothesis distribution variance provided in Section 8.2.8 correcting for ties.
^cP-value obtained by Mann-Whitney U Test. P-value boundary of 0.05 is used to conclude statistical significance.

Table 54: ITT Analysis of DOOR Based on Average Ordinal Clinical Outcome from Study Day 1 Through Study Day 11 - ITT Analysis Population with Complete Data

Statistic	Value
Subjects with non-missing DOOR– n (%)	x (x)
Pr(Higher DOOR in Placebo Arm) ^a (95% CI) ^b	x.xx (x.xx, x.xx)
P-value ^c	x.xxx

Note: DOOR was calculated based on subjects with non-missing OCO at atleast one of the timepoints. Missing values were ignored when calculating average OCO.
 
^aProbability of Higher DOOR in Placebo Arm + 0.5 Probability of Equal DOOR. CI obtained through inversion of the F-test used to compute the p-value.
 
^bObtained through using inversion of the Mann-Whitney U test with a normal approximation and assuming the null hypothesis distribution variance provided in Section 8.2.8 correcting for ties.
 
^cP-value obtained by Mann-Whitney U Test. P-value boundary of 0.05 is used to conclude statistical significance.
	

Table 55: ITT Analysis of DOOR Based on Average Ordinal Clinical Outcome from D5V, D11V, and D28V - ITT Analysis Population with Complete Data

Statistic	Value

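### The DOOR confidence intervals are built on the Mann-Whitney null variance, although the antibiotic tie-break makes the arms differ by design; the width error is usually small. The tie term is misprinted, and the planned bootstrap interval has no column in Table 48.

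*SAP*

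**What the plan says.** SAP 8.2.8 computes a Mann-Whitney U statistic in each of 20 imputed datasets and combines them by Rubin's rules. On the within-imputation term it states: "Correcting for ties, the formula for the within imputation variance of the Mann-Whitney U statistic is" n1·n2/12 × [(N+1) − Σ(M³−M)/(N(N+1))], where N = n1+n2 and M is the size of each tied group. The total variance T feeds both the p-value and the interval: "A corresponding 95% CI for U will be computed using the overall test statistic W through the inversion of the F-test". The printed limits are the mean U plus or minus the square root of T times an F quantile, divided by n1·n2. Table 37 (ITT) and Table 38 (ATP-5) report this at Day 5. Section 8.3.3 carries the method to Day 11 (Tables 46 and 47).

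The complete-data ATP analyses (Table 48) use the same variance in a plus-or-minus 1.96 interval. Section 8.2.8 adds a second interval for them: "Confidence intervals for the DOOR probability using a non-parametric bootstrap", with 10,000 resamples.

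The footnotes to Tables 53 to 55 describe the variance as "assuming the null hypothesis distribution variance provided in Section 8.2.8 correcting for ties". Protocol 11.4.2 item 9 (Day 5) and 11.4.3 item 3 (Day 11) likewise call for an interval obtained by inverting the test of the null hypothesis.

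Under SAP 6.5.5, active study drug counts towards days of antibiotic use and placebo does not. Under 3.3.5 and 6.5.6, fewer antibiotic days wins when two subjects share an OCO.

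**The concern.** The Mann-Whitney variance is derived for two arms with the same distribution. It belongs in the denominator of the test. The SAP interval is centred on the estimate and holds that variance fixed, so it is in effect a Wald interval with the wrong variance whenever the arms differ.

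Here the endpoint nearly guarantees that they differ. A typical adherent azithromycin subject has about 5 antibiotic days and a typical placebo subject has 0, so most between-arm ties on OCO go to placebo even when the drug makes no clinical difference. DOOR at Day 5 is a named secondary outcome, and its interval is the reported precision of that result.

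Two drafting faults sit beside this. The tie correction has the wrong denominator. The interval that avoids the null variance, the bootstrap, is promised in the text but has nowhere to appear in the table shells.

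**Working it through.** **Inputs from the documents.** About 337 per arm randomized and 280 per arm in ATP-5 (protocol section 5); 16.9% loss and 57.6% improved per arm (protocol 11.2); 95% intervals; antibiotic days as tie-breaker. The documents state no DOOR power, expected DOOR probability or interval width, so there is no DOOR figure to reproduce. The sample size inflation does reproduce: 560/(1−0.169) = 673.9, or 674.

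**Assumed, because not given.** The OCO split: 0-50% of improved subjects have a solicited event (divided 60/30/10 over OCO 2, 3, 4), 0-30% of non-improved subjects have a medically attended event (divided 75/25 over OCO 6, 7), and no deaths. Antibiotic days are 0 on placebo and 5 on azithromycin.

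**Is it the null variance?** At 280 per arm, 10,000 permutations of one pooled dataset gave a variance of U of 3.55 million. The SAP formula gave 3.53 million. It is.

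**Expected DOOR probability with no clinical difference.** If every between-arm OCO tie breaks for placebo, theta = 0.5 + 0.5 Σp², where p are the OCO probabilities. With everyone in OCO 1 or 5: 0.5 + 0.5(0.576² + 0.424²) = 0.756. With the widest spread assumed: 0.610.

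**Width, worked for the two-category case.**
- Null variance × n: (1/6)(1 − Σw³), with pooled weights 0.288, 0.288, 0.212, 0.212. This is (1 − 0.0668)/6 = 0.1555.
- Correct variance × n: the sum over arms of the variance of each subject's probability of a favourable comparison (placement). Placebo: 0.576 × 0.424 × (1 − 0.424)² = 0.0810. Azithromycin: 0.576 × 0.424 × (1 − 0.576)² = 0.0439. The sum is 0.1249.
- SE ratio: √(0.1555/0.1249) = 1.116. At 337 per arm the half-widths are 1.96√(0.1555/337) = 0.0421 (SAP) and 1.96√(0.1249/337) = 0.0377 (correct).

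**The same calculation over other splits.** Approximate coverage is 2Φ(1.96 × ratio) − 1.

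| Setting (placebo vs azithromycin improved) | theta | SAP/correct SE | Coverage |
|---|---|---|---|
| 57.6% vs 57.6%, all in OCO 1 or 5 | 0.756 | 1.116 | 97.1% |
| same rates, 10% solicited events, 10% attended | 0.709 | 1.047 | 96.0% |
| same rates, 20% and 10% | 0.683 | 1.029 | 95.6% |
| same rates, 30% and 20% | 0.648 | 1.012 | 95.3% |
| same rates, 50% and 30% | 0.610 | 1.009 | 95.2% |
| 45.1% vs 57.6%, all in OCO 1 or 5 | 0.684 | 1.00 | 95.0% |
| 45.1% vs 57.6%, 25% and 10% | 0.609 | 0.961 | 94.0% |

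Simulation of 20,000 trials agrees. With placebo 12.5 points worse the ratio was 0.952-0.955 and coverage 94.0-94.1%. A placement-based variance gave coverage of 94.7-95.3%. In one simulated dataset at 280 per arm (estimate 0.683), the SAP interval was 0.636-0.730 and the bootstrap 0.635-0.727.

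**Tie term.** If all N subjects tie, the variance must be 0. The SAP bracket gives (N+1) − (N³−N)/(N(N+1)) = (N+1) − (N−1) = 2. Dividing by N(N−1) instead gives (N+1) − (N+1) = 0. The slip changes the SE by under 0.02%.

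**Table 48.** The 8.2.8 text names two intervals for the complete-data analysis and sends the results to Table 48. The shell has one interval column, the normal approximation. No other shell shows a bootstrap interval for this quantity; Figures 21 and 22 bootstrap a DOOR probability that ignores antibiotic duration.

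**The case against.** The effect is small, and that stands. The tables print the DOOR probability to two decimals. The half-width error is 0.0044 in the extreme two-category case, and the SAP half-width falls short by at most about 0.002 when placebo is worse. The between-imputation term in T, left out of the figures above, dilutes the error further in Tables 37, 38, 46 and 47. Only the primary analysis decides non-inferiority (SAP 8.1.1), and Table 37 itself asks readers to weigh the DOOR components and sensitivity analyses.

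The method also follows the protocol and keeps the interval consistent with the test, where "P-value boundary of 0.05 is used to conclude statistical significance". That is a fair reason for the present choice. It does not make the variance right for an interval.

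A reader might infer more than the documents support:

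- *That the DOOR intervals are badly wrong.* Coverage of about 94-97% does not bear this out.
- *That distance from 0.5 drives the error.* It does not by itself. With 80% improved, simulation gave theta 0.703 and a ratio of 0.99-1.00, while at 57.6% improved a theta of 0.699 had a ratio of 1.047.
- *That antibiotic days break every tie.* Within-arm ties remain, as do between-arm ties where antibiotic days match.
- *That the bootstrap was dropped.* It is planned in the text; what is missing is its column.
- *That all DOOR tables are affected alike.* Tables 54 and 55 and the first part of Table 53 use no antibiotic tie-break, so this mechanism does not reach them.

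**Conclusion.** The point holds as a modest technical correction. The SAP uses a variance that is valid for testing 0.5 to form intervals in a setting where the arms' DOOR distributions differ by design. With similar clinical outcomes, the complete-data interval is about 1-5% too wide in most settings, and about 12% if everyone falls in OCO 1 or 5. With placebo 12.5 points worse, it is about 0-5% too narrow. These sizes rest on assumed OCO splits and on 0 versus 5 antibiotic days, at 337 per arm and, for azithromycin, 57.6% improved. The null variance remains the right one for the p-value. The misprinted tie term and the missing Table 48 column are plain errors that need no assumptions; the first is numerically negligible.

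**What to change.** - Keep the null variance for the p-value only, and correct the tie denominator to (n1+n2)(n1+n2−1) in both places where 8.2.8 prints it.
- For the intervals in Tables 37, 38, 46 and 47, use a placement-based (DeLong-type) variance of U as the within-imputation term and combine by Rubin's rules.
- Add the bootstrap interval already planned, or a placement-based one, as a column in the Table 48 shell.
- Record the change against protocol 11.4.2 item 9 and 11.4.3 item 3, which prescribe inversion of the null test.

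The cost is SAP wording, a documented departure from the protocol text and standard code; no new data are needed. One small downside: the interval and the p-value may occasionally disagree when the result is near 0.5, and a table footnote should say so.

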8.2.9. Analysis of Solicited Events at D5V Using ATP-5 Analysis Population

Results of the analysis of solicited events at D5V, a component of DOOR, will be presented using forest plots of 95% CIs for the risk difference of each solicited event and the risk difference for placebo compared to azithromycin of any solicited event, for each severity threshold (mild or greater, moderate or greater, or severe) in [Figure 2](#), [Figure 3](#), and [Figure 4](#). Results will also be reported in tables [Table 56](#), [Table 57](#), and [Table 58](#). Tests for differences in proportions between treatment arms will be given by Fisher's exact tests. Since Fisher's test cannot be inverted, there is no corresponding CI. Therefore, the Miettinen-Nurminen method will be used to compute all 95% CIs for risk differences. Note that the CI results might not be consistent with the p-value from Fisher's exact test.

8.2.10. Analysis of Medically Attended Events at D5V Using ATP-5 Analysis Populations

A forest plot of 95% CIs for the risk difference of one or more visits to an ED, one or more visits to an outpatient clinic, or one or more visits to an urgent care center or one or more hospitalizations for persistent or worsening LRTI at any time after randomization will be produced for D5V using ATP-5 analysis population in [Figure 8](#) and results will also be presented in [Table 43](#) to include a p-value from Fisher's exact test. Since Fisher's test cannot be inverted, there is no corresponding CI. Therefore, the Miettinen–Nurminen method will be used to compute all 95% CIs for risk differences. Note that the CI results might not be consistent with the p-value from Fisher's exact test. [Listing 19](#) contains all medically attended visits while [Listing 20](#) provides a listing of all hospitalizations.

8.2.11. Improvement in Qualifying Symptoms or Vital Signs at D5V Using ATP-5 Analysis Population

The proportions of subjects exhibiting improvement in one qualifying symptom (cough, sputum production, chest pain, or difficulty breathing) or vital sign (temperature, pulse, respiratory rate, or pulse oximetry) at Visit 3 compared to baseline will be computed for placebo versus azithromycin along with associated 95% CIs using ATP-5 population. A forest plot of 95% CIs for the difference in proportions of subjects with improvement in any symptom or sign, any symptom, any sign, at least two symptoms or signs, and each individual symptom or sign will be provided in [Figure 10](#). Results will also be reported in [Table 41](#), and tests for differences in proportions between treatment arms will be given by Fisher's exact tests. Since Fisher's test cannot be inverted, there is no corresponding CI. Therefore, the Miettinen–Nurminen method will be used to compute the 95% CIs for risk differences. Note that the CI results might not be consistent with the p-value from Fisher's exact test.

